## **6.2 DATA SHARING PLANS**

### 6.2.1 Human Data Sharing Plan

#### **What data will be shared?**

I will share human data generated in this research for future research as follows:

- Coded, linked data in an NIH-funded or approved public repository.
- Coded, linked data in another public repository.
- Coded, linked data in BTRIS (automatic for activities in the Clinical Center).
- Identified or coded, linked data with approved outside collaborators under appropriate agreements.

#### **How and where will the data be shared?**

Data will be shared through:

- An NIH-funded or approved public repository, [clinicaltrials.gov](http://clinicaltrials.gov).
- BTRIS (automatic for activities in the Clinical Center).
- Publication and/or public presentations.

#### **When will the data be shared?**

- Before publication.
- At the time of publication or shortly thereafter.

### 6.2.2 Genomic Data Sharing Plan

No genomic data will be collected.

## **6.3 TOXICITY CRITERIA**

The following adverse event management guidelines are intended to ensure the safety of each patient while on the study. The descriptions and grading scales found in the revised NCI Common Terminology Criteria for Adverse Events (CTCAE) version 5.0 will be utilized for AE reporting. All appropriate treatment areas should have access to a copy of the CTCAE version 5.0. A copy of the CTCAE version 5.0 can be downloaded from the CTEP web site ([http://ctep.cancer.gov/protocolDevelopment/electronic\\_applications/ctc.htm#ctc\\_50](http://ctep.cancer.gov/protocolDevelopment/electronic_applications/ctc.htm#ctc_50)).

## **7 NIH REPORTING REQUIREMENTS/DATA AND SAFETY MONITORING PLAN**

### **7.1 DEFINITIONS**

Please refer to definitions provided in Policy 801: Reporting Research Events found [here](#).

## **7.2 OHSRP OFFICE OF COMPLIANCE AND TRAINING / IRB REPORTING**

### **7.2.1 Expedited Reporting**

Please refer to the reporting requirements in Policy 801: Reporting Research Events and Policy 802: Non-Compliance Human Subjects Research found [here](#).

- Reports referenced in Policy 801 are made to the IC Specific IRB rather than to the OHSRP Office of Compliance and Training.
- Section 5.2 of the Policy 801 does not apply.
- Policy 802 does not apply.

### **7.2.2 IRB Requirements for PI Reporting at Continuing Review**

Please refer to the reporting requirements in Policy 801: Reporting Research Events found [here](#).

## **7.3 NCI CLINICAL DIRECTOR REPORTING**

Problems expeditiously reported to the OHSRP/IRB in iRIS will also be reported to the NCI Clinical Director. A separate submission is not necessary as reports in iRIS will be available to the Clinical Director.

In addition to those reports, all deaths that occur within 30 days after receiving a research intervention should be reported via email to the Clinical Director unless they are due to progressive disease.

To report these deaths, please send an email describing the circumstances of the death to [name] at [[contact]](mailto:[contact]) within one business day of learning of the death.

## **7.4 NIH REQUIRED DATA AND SAFETY MONITORING PLAN**

### **7.4.1 Principal Investigator/Research Team**

The clinical research team will meet on a regular basis (weekly) when patients are being actively treated on the trial to discuss each patient.

All data will be collected in a timely manner and reviewed by the principal investigator or a lead associate investigator. Events meeting requirements for expedited reporting as described in Section **7.2.1** will be submitted within the appropriate timelines.

The principal investigator will review adverse event on each patient to ensure safety and data accuracy. The principal investigator will personally conduct or supervise the investigation and provide appropriate delegation of responsibilities to other members of the research staff.

## **8 STATISTICAL CONSIDERATIONS**

### **8.1 STATISTICAL HYPOTHESIS**

Primary Endpoint:

- Determine if confocal endoscopic microscopy (CEM) affords greater sensitivity for detection of SRC foci in CDH1 germline mutation carriers compared to the current method of standard white light endoscopy.

Secondary Endpoint:

- Define the false negative rate of CEM detection of SRC foci in those patients who choose to undergo prophylactic total gastrectomy with permanent pathologic analysis.

## **8.2 SAMPLE SIZE DETERMINATION**

Subjects who are carriers of a CDH1 mutation and participate in this trial will undergo an EGD and detailed gastric mapping along with confocal laser microscopy. Based on the historical data from NIH, 17 patients who were CDH1 mutation carriers and who underwent an EGD and detailed gastric mapping resulted in 4 with signet ring foci detected. All 4 of these patients eventually were found to have gastric cancer after undergoing a prophylactic gastrectomy. An additional 18 patients who had prophylactic gastrectomy out of 39 who had conventional random biopsies yielded 8 patients with gastric cancer.

Based on the current historical rate of 4/17 (23.5%) of mapped patients who had signet ring foci detected, it would be desirable to see if use of confocal laser microscopy could increase this detection rate substantially. With 36 patients undergoing EGD with detailed gastric mapping and confocal laser microscopy, there would be 89% power to rule out a 24% rate of signet ring detection in favor of a rate of detection consistent with 45%, with a one-sided 0.10 significance level exact binomial test. In practice, if 36 patients would undergo the procedure described and if 13/36 (36.1%) would have signet ring foci identified, then the lower one-sided 90% confidence bound on 13/36 is 25.3%, which would demonstrate statistically greater detection in the subjects tested compared to the historical fraction of 4/17 (23.5%). In addition, the upper one-sided 90% confidence bound on 13/36 is 48.2%, which demonstrates that 13/36 could be shown to be consistent with as great as a 45% detection rate.

It is expected that 18-20 patients may enroll on this study per year. Thus, to enroll 36 evaluable patients, approximately 24 months is the expected accrual period. To allow for a small number of inevaluable patients, the accrual ceiling will be set at 40 patients.

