Our group has substantial experience evaluating HDGC syndrome patients with data that support the inadequacy of current endoscopic surveillance methods. As of November 2017, we evaluated 54 patients with predisposition to gastric malignancy at the NIH. Of the 54 patients evaluated, 40 (74%) had a primary genetic abnormality predisposing to gastric malignancy with the remainder having strong family history. All patients were Caucasian, with a majority being female (66%) and a mean age of 44 years. Subjects were screened either through standard upper endoscopy (EGD) with a combination of random and targeted biopsies, or later through a systematic gastric mapping protocol developed by Yao.[12] Of the 56 EGDs performed, 17 (30%) were performed via detailed gastric mapping with resultant 88 individual biopsies in 22 distinct locations in the stomach. Of the remaining 39 (70%) standard EGDs, targeted biopsies of endoscopic abnormalities and random biopsies from the antrum and body were performed. In subjects undergoing systematic gastric mapping, signet ring cells were identified in 4 patients (24%), whereas all 39 standard EGD biopsies were absent of signet ring cells (0%). With regard to long-term follow up, in 22 patients that subsequently underwent prophylactic total gastrectomy, malignancy was identified by histology in 12 (55%) of cases. In the 4 subjects that underwent systematic gastric mapping followed by total gastrectomy, biopsies obtained during gastric mapping matched gastrectomy specimen pathology in all cases (100%). Comparatively, in the 18 subjects that underwent standard endoscopy and gastrectomy, 8 cases of malignancy were identified on gastrectomy specimen pathology (44%). See flowchart below. These preliminary results suggest that while comprehensive gastric mapping biopsies may be superior at detecting early malignancy when compared to standard EGD, the overall detection rate remains too low to recommend surveillance over prophylactic total gastrectomy with confidence.

Similarly, a retrospective study of 23 patients with a CDH1 mutation also demonstrated that EGD is not an adequate screening modality. Of the 23 patients, only 2 were found to have SRC foci on EGD with biopsy. All 23 patients underwent a prophylactic total gastrectomy. On final pathology, 22/23 patients were found to have foci of SRCs. This means that screening with EGD only had a detection rate of 9%.[\[13\]](#)

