## **3 STUDY IMPLEMENTATION**

### **3.1 STUDY DESIGN**

This is a Phase II single arm study designed to evaluate the efficacy of CEM to detect signet ring cell foci within the gastric mucosa of patients with hereditary diffuse gastric cancer syndrome.

At the time of endoscopy, all patients will undergo white-light, upper endoscopy with systematic gastric mapping according to our current practice pattern and as outlined by IGCLC [12] (Section 3.2.2). In addition, during this endoscopy patients will undergo CEM using the Cellvizio probe (Mauna Kea Technologies) to scan the same anatomic zones as evaluated in the systematic gastric mapping approach (Section 3.2.3). Any abnormal areas visualized with the CEM probe will be biopsied. Patients are informed of the risks of endoscopy such as gastrointestinal bleeding and perforation. The standard gastric mapping requires approximately 30 minutes of general anesthesia time. The addition of CEM adds another 30 minutes of general anesthesia but no increase in risk of general complications such as bleeding or perforation.

All biopsies are sent to Laboratory of Pathology (see Section 5.1.1). In patients co-enrolled to protocol 13C0176, leftover biopsy samples will be used for research as described in 13C0176.

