#### **3.2.2 White-light, Upper Endoscopy**

At the time of endoscopy, all patients will undergo white-light, upper endoscopy with systematic gastric mapping according to IGCLC guidelines.[8] The anatomic zones are outlined below. From each of the five zones, 6 cold forceps biopsies and photos will be obtained. The total number of biopsies will be thirty. Any visibly abnormal areas will also be biopsied.

1. Antrum
2. Transitional Zone (antrum-body)
3. Body
4. Fundus

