## 5. Cardia

### 3.2.3 CEM Analysis

Patients will also undergo CEM analysis of gastric zones using the Cellvizio probe (Mauna Kea Technologies). Abnormal mucosa visualized will have images digitally captured and biopsied.

- Antrum (antegrade view): 4 quadrants (Anterior [A], Lesser curve [L], Posterior [P], Greater curve [G])
- Lower body (antegrade view): 4 quadrants [A, L, P, G]
- Middle-upper body (antegrade view): 4 quadrants [A, L, P, G]
- Fundus-cardia (retroflex view): 4 quadrants [A, L, P, G]
- Middle-upper body (retroflex view): 3 quadrants [A, L, P]
- Incisura (retroflex view): 3 quadrants [A, L, P]

Patients will receive the contrast agent fluorescein prior to endoscopy if no known allergy to fluorescein is documented. Patients who cannot receive fluorescein (e.g. pregnancy or allergy) will have CEM performed in the absence of this contrast agent.

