#### **8.4.1 Analysis of the Primary Endpoints**

The fraction of patients who undergo the EGD and detailed mapping along with confocal endoscopic microscopy and have signet ring cell foci identified will be reported along with 80% and 95% two-sided confidence intervals.

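### The 24% reference rate comes from 88-biopsy mapping but section 3.2.2 specifies 30 biopsies; if 30 are taken, a negative result cannot separate reduced sampling from no benefit of CEM

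*Combined protocol and SAP*

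**What the plan says.** **Reference rate.** Section 8.2 starts from "Based on the current historical rate of 4/17 (23.5%) of mapped patients who had signet ring foci detected" and claims "89% power to rule out a 24% rate of signet ring detection in favor of a rate of detection consistent with 45" per cent, with 36 patients and a one-sided 0.10 exact binomial test. The success boundary is 13/36.

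**How the reference patients were mapped.** Section 1.2 says that the 17 procedures were "performed via detailed gastric mapping with resultant 88 individual biopsies in 22 distinct locations in the stomach".

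**How trial patients will be mapped.** Section 3.2.2 asks for six biopsies in each of five zones (antrum, transitional zone, body, fundus, cardia) plus any visible abnormality: "The total number of biopsies will be thirty". It cites reference 8. Section 3.1 describes "systematic gastric mapping according to our current practice pattern and as outlined by IGCLC [12"; reference 12 is the source that section 1.2 gives for the historical mapping protocol.

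**Where CEM looks.** Section 3.1 says the probe is used "to scan the same anatomic zones as evaluated in the systematic gastric mapping approach". Section 3.2.3 lists 4+4+4+4+3+3 = 22 sites. It has an incisura site, no transitional zone, and one joint entry for two of the mapping zones: "Fundus-cardia (retroflex view): 4 quadrants [A, L, P, G".

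**What is analysed.** Under section 8.4.1 the fraction of patients who have "detailed mapping along with confocal endoscopic microscopy and have signet ring cell foci identified will be reported" with 80% and 95% intervals. Section 8.4 describes the same combined fraction. No section plans a mapping-only or CEM-only fraction, or says that biopsies are recorded by what prompted them.

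**The concern.** The primary objective is whether CEM is more sensitive than the current method. The trial has one arm and one combined endpoint, so the only comparison with mapping is the one against 24%. That works only if 24% is about what the mapping done in this trial would find by itself. Section 8.2 calls the historical and the trial procedure by the same name and does not mention that the biopsy counts differ, 88 against 30.

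If the 30-biopsy scheme is used and finds fewer patients, the first part of any CEM gain goes into making up that shortfall. A result below 13/36 then has two readings, and nothing in the planned analysis tells them apart. The 89% would also not be the power to detect a CEM gain over the mapping actually performed.

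**Working it through.** **1. The plan's own figure.** Inputs from section 8.2: n = 36, null 0.24, alternative 0.45, one-sided 0.10, exact binomial.

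- P(X ≥ 12 | 0.24) = 0.133, above 0.10. P(X ≥ 13 | 0.24) = 0.0703. The boundary is therefore 13.
- P(X ≥ 13 | 0.45) = 0.893.

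The 89% is right on its own inputs.

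**2. The sampling difference.** 88/22 = 4 biopsies per location, which supports reading 88 as a per-procedure count. 30/88 = 34%.

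**3. What 30 biopsies might find.** The documents give no such rate, so this step is illustration. Let *prev* be the share of patients with SRC. It is taken as 0.55 to 1.0, because section 1.2 reports 12/22 (55%) in the centre's own gastrectomies and 22/23 in a retrospective series.

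- Equal, independent chance per biopsy: q = 1 − (1 − (4/17)/prev)^(1/88); yield = prev × (1 − (1 − q)^30). Result: 8.7% at prev 1.0 and 9.5% at prev 0.55.
- Chance varying between patients: q follows a Beta(a, b) distribution, with b chosen so that 88 biopsies give 4/17. At prev 1.0 / 0.55 the yield is 12.6% / 16.8% for a = 0.2, 15.9% / 20.0% for a = 0.1, and 19.3% / 21.8% for a = 0.05 (very strong clustering).

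The assumed range is thus about 9% to 22%.

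**4. Chance of at least 13/36 if CEM adds nothing.** 7.0% at a 24% yield, 1.8% at 20%, 0.5% at 17%, 0.002% at 10%. False positives become rarer.

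**5. CEM-only patients needed on average to reach 13,** from 13 − 36 × yield: 4.4 at 24%, 5.8 at 20%, 6.9 at 17%, 9.8 at 9%.

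**6. Chance of at least 13/36 if CEM works as planned.** Two models of the gain are used:

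- Fixed: combined rate = yield + 0.21.
- Independent detection: combined rate = yield + (prev − yield) × s, with s set so that 24% rises to 45%. Then s = 0.21/(1 − 0.24) = 0.276 at prev 1.0, and s = 0.21/(0.55 − 0.24) = 0.677 at prev 0.55.

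| Assumed mapping yield | Fixed +21 points | Independent, prev 1.0 | Independent, prev 0.55 |
|---|---|---|---|
| 24% | 89% | 89% | 89% |
| 22% | 84% | 86% | 88% |
| 20% | 78% | 81% | 86% |
| 17% | 65% | 74% | 83% |
| Equal-chance value for that prev (8.7% or 9.5%) | 25% (at 8.7%) | 45% (at 8.7%) | 75% (at 9.5%) |

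**7. Precision of the reference.** The exact 95% interval for 4/17 is 6.8% to 49.9%.

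**The case against.** **There is a CEM-specific output.** Section 8.4.2 plans a CEM false negative rate against gastrectomy pathology. A very high or very low value would bear on whether CEM works. But it covers only patients who choose gastrectomy, and it does not measure what CEM adds to mapping. It does not separate the two readings of a negative primary result.

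**The loss may be small.** The low yields assume equal, independent biopsies. The fixed 21-point model holds the gain constant although CEM would have more left to find. With strong clustering, or with independent detection at 55% prevalence, most of the power survives. This stands: the size of the loss is unknown, and the figures above are illustration.

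**The scheme may not have changed.** The 22 CEM sites equal the 22 historical locations in number, and section 3.1 cites the historical source. The zone differences may be partly a matter of labels. If mapping still follows the historical protocol, the mismatch largely disappears, but section 3.2.2 then contradicts it.

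**Other causes matter too.** Section 8.2 describes the reference patients as CDH1 carriers, while section 2.1.1 also admits CTNNA1 and PALB2 carriers and mutation-negative patients. The reference is imprecise, and a combined endpoint would be hard to interpret even with 88 biopsies. All of this is true. These are further reasons why a negative result would be ambiguous; none removes this one. They also mean that a low mapping-only yield could not be put down to biopsy number alone.

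**Conclusion.** The concern holds and should be fixed. The sections disagree on the mapping scheme, and section 8.2 takes its null from a protocol with almost three times the biopsies that section 3.2.2 specifies. The power calculation contains no arithmetic error, and a positive result is not inflated.

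The weakness is in a negative result. If the 30-biopsy scheme applies and its yield is below 24%, a CEM effect of the planned size reaches 13/36 with a probability of 25% to 88%, depending on the yield and the model, instead of 89%. A failure could not be interpreted from the planned output.

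This rests on reading 88 as a per-procedure count and on assumed 30-biopsy yields. If the true yield were close to 24%, the stated power would stand. The contradiction between the sections is certain; the size of its effect is not.

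**What to change.** 1. Reconcile sections 1.2, 3.1, 3.2.2, 3.2.3 and 8.2 on which mapping scheme and which zones apply. This review does not say which.
2. State in section 8.2 that 4/17 came from an 88-biopsy, 22-location protocol.
3. Record each biopsy as mapping, visible lesion or CEM-triggered. This has to be done at endoscopy, as it may not be recoverable later.
4. In section 8.4.1, next to the combined rate, report the mapping-only yield and the fraction of patients whose SRC was found only by a CEM-triggered biopsy. Give each the planned 80% and 95% intervals, as descriptive results without a new test.
5. If the 24% null is kept and the schemes differ, describe the 89% as power for an absolute 45% rate against the historical rate, not for CEM's increment.

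The added estimate is informative with 36 patients. With 0/36 CEM-only patients, the upper limit of the two-sided 95% interval is 1 − 0.025^(1/36) = 9.7%. With 7/36 (19.4%), the exact 95% interval is 8.2% to 36.0%.

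The cost is protocol wording, one field on the data form and the pathology request, and two extra proportions. Sample size, primary test and procedures stay as they are. The plan would give a less favourable account of what the 89% means, and the CEM-only estimate will have wide intervals.

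### Section 8.2 reads 13/36 as statistically greater detection than the historical 4/17, but its test only excludes a fixed 24% and ignores the sampling error in 17 patients

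*Combined protocol and SAP*

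**What the plan says.** Section 8.2 of the combined protocol and SAP takes its benchmark from the institution's own series: "Based on the current historical rate of 4/17 (23.5%) of mapped patients who had signet ring foci detected". Section 1.2 gives the same count; among patients who had systematic mapping, "signet ring cells were identified in 4 patients (24" per cent).

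The design is then stated as a one-sample test: "there would be 89% power to rule out a 24% rate of signet ring detection in favor of a rate of detection consistent with 45" per cent, using an exact binomial test at one-sided 0.10 with 36 patients.

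To illustrate a positive result, the section says that "the lower one-sided 90% confidence bound on 13/36 is 25.3" per cent, and draws the conclusion "which would demonstrate statistically greater detection in the subjects tested compared to the historical fraction of 4/17 (23.5" per cent).

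No interval or other measure of uncertainty for 4/17 is given in Sections 1.2, 8.2 or 8.4. Section 8.4.1 plans to report the new fraction with its own 80% and 95% intervals.

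The two mapping procedures are described differently. In the historical series the mapped examinations "were performed via detailed gastric mapping with resultant 88 individual biopsies in 22 distinct locations in the stomach" (Section 1.2). In the trial, mapping covers five zones and "The total number of biopsies will be thirty", plus any visibly abnormal areas (Section 3.2.2).

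**The concern.** A one-sample test against a fixed rate treats that rate as known. Here it was estimated from 17 patients. Excluding the number 24% is not the same as showing a higher detection rate than historical mapping, because the true historical rate could lie well above or below 24%.

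This matters because the study has a single arm and a comparative primary objective. The sentence in Section 8.2 is the only place where the plan says what count would support the comparison, so a results report is likely to repeat it. As worded, it would let 13/36 be presented as statistical superiority over the historical series.

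**Working it through.** **Inputs.** n = 36, null rate 24%, alternative 45%, one-sided 0.10 exact binomial test, example result 13/36 (all Section 8.2); historical count 4 of 17 (Sections 1.2 and 8.2); 88 historical biopsies (Section 1.2) and 30 trial mapping biopsies (Section 3.2.2).

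**Step 1: reproduce the plan.** With X ~ Binomial(36, p):

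- P(X ≥ 12 | p = 0.24) = 0.133, above 0.10.
- P(X ≥ 13 | p = 0.24) = 0.070, so 13/36 is the smallest rejecting count.
- P(X ≥ 13 | p = 0.45) = 0.893, matching the stated 89%.
- The lower one-sided 90% exact bound on 13/36 is the 0.10 quantile of Beta(13, 24) = 0.2532, matching 25.3%.
- The upper bound is the 0.90 quantile of Beta(14, 23) = 0.4815, or 48.1% against the printed 48.2%. This is immaterial.

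**Step 2: the uncertainty the plan leaves out.** Exact (Clopper-Pearson) limits for 4/17 are the a quantile of Beta(4, 14) and the 1 − a quantile of Beta(5, 13):

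- 80% interval (a = 0.10): 10.7% to 41.6%.
- 95% interval (a = 0.025): 6.8% to 49.9%.

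Both include 13/36 = 36.1%.

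**Step 3: how the error rate depends on the benchmark.** Let p be the true detection rate of mapping as performed in this trial, and suppose CEM adds nothing. The chance of crossing the cutoff is then P(X ≥ 13 | n = 36, p). The last column shows how compatible each rate is with the history if historical mapping had the same rate: P(Y ≤ 4 | n = 17, p).

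| True rate p | P(13 or more of 36), no improvement | P(4 or fewer of 17) |
|---|---|---|
| 20% | 0.018 | 0.758 |
| 24% | 0.070 | 0.612 |
| 25.3% | 0.100 | 0.562 |
| 30% | 0.263 | 0.389 |
| 35% | 0.507 | 0.235 |

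The error stays at or below 0.10 only while p is at or below 25.3%, which is 25.3 − 23.5 = 1.8 points above the observed historical fraction. At the 80% limits of 4/17 the chance runs from below 0.001 (10.7%) to 0.80 (41.6%). Seventeen patients do not separate the rates in the table. The effect runs both ways: below 24% the test is conservative.

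**Step 4: the assumption that links the two columns.** Reading the columns together assumes that trial mapping detects as often as historical mapping. With 30 biopsies instead of 88, the rate without CEM would, other things equal, tend to be lower. As an extreme illustration, assume independent biopsies of equal yield, so that the rate with 30 is 1 − (1 − h)^(30/88), where h is the historical rate. Then h = 23.5%, 30%, 35% and 41.6% become 8.7%, 11.4%, 13.7% and 16.8%, and P(X ≥ 13 of 36) is below 0.005 at each. Foci within one stomach are unlikely to be sampled independently, so this exaggerates the drop. It does show the direction.

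**The case against.** A fixed benchmark is a usual device in a single-arm phase II study. The sentence before the disputed one names the test and the fixed 24%. Read literally, the historical fraction can mean the number 23.5%, and 25.3% does exceed it. Numerator and denominator are printed, Section 1.2 calls the historical results preliminary, the 13/36 sentence is an illustration, and Section 8.4.1 plans only to report the new fraction with intervals. All of this stands, and it is why the point concerns wording and not design. It does not rescue the clause: a statement of statistically greater detection compared with a count from 17 patients can naturally be read as superiority over that series, and nothing elsewhere limits it.

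Three stronger readings are tempting, and the documents support none of them.

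- *The sample size or power is wrong.* Both reproduce for the test that is stated.
- *The trial should be judged by a two-sample comparison of 13/36 with 4/17.* The plan proposes no such test, so its 0.10 level should not be applied to one, and p-values from one would answer a question the plan does not pose.
- *The false-positive risk is 26% or 51%, and the biopsy difference makes it worse.* Those figures are conditional on true trial-mapping rates of 30% and 35%. Taking fewer biopsies would tend to lower the rate without CEM, and so to lower the chance of a false positive.

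**Conclusion.** The concern holds as a fault of inference in one sentence of Section 8.2. The stated test supports only the conclusion that 13/36 excludes a fixed 24% at one-sided 0.10. It does not support statistical superiority over the historical series, whose exact 80% interval of 10.7% to 41.6% includes the 36.1% result.

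The size depends on a quantity that 17 patients barely constrain. With no improvement from CEM, the chance of reaching the cutoff is 0.02, 0.07, 0.26 or 0.51 if mapping as done in the trial truly detects 20%, 24%, 30% or 35%. These figures assume independent patients with a common detection rate and cover sampling error only. They carry over from the historical series only if 30-biopsy mapping detects as often as 88-biopsy mapping did; if it detects less often, the risk is smaller. The documents do not show which of these rates applies, so this is a range and not an estimate of the trial's error rate.

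The sentence should be corrected because it sets what may be claimed at the success threshold. The design does not need to change.

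**What to change.** In Section 8.2, replace the clause on statistically greater detection with: *13/36 would exclude a fixed benchmark detection rate of 24% at one-sided 0.10.* Drop the claim of statistical superiority over the historical series.

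Then add: *The benchmark comes from 4/17 (exact 80% CI 10.7-41.6%, 95% CI 6.8-49.9%). If the true detection rate of mapping as performed in this trial is 20%, 24%, 30% or 35%, the chance of 13 or more of 36 with no improvement from CEM is 0.02, 0.07, 0.26 or 0.51. These rates refer to mapping with 30 biopsies; the historical series used 88, and fewer biopsies would tend to lower the detection rate without CEM.*

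Keep n = 36, the 13/36 cutoff, the one-sided 0.10 level and the 89% power against the fixed benchmark. Do not add a two-sample test.

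The cost is a few sentences in one section, with no change to procedures, accrual or the analysis in Section 8.4. The only downside is a less favourable claim if the result is 13/36.
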